5 STUDY INTERVENTIONS	

14	4 F	PUBLICATION OF RESEARCH FINDINGS	
1	3 (COMMITTEES	
1:	2 E	THICAL CONSIDERATIONS	
	11.1 11.2	Institutional Review Board (IRB) Review Participant Confidentiality	
1	1 F	PARTICIPANT RIGHTS AND CONFIDENTIALITY	
	10.4	Data Use Agreements	
	10.3	Data Management	
	10.2	Data Confidentiality	
	10.1	Onsite Data Collection	
1	DI	DATA COLLECTION AND QUALITY ASSURANCE	
	9.5	Data Analyses	
	9.4	Outcomes	
	9.3	Interim analyses and Stopping Rules	
	9.1 9.2	General Design Issues Sample Size and Randomization	
9			
8			
	7.5.	Safety Monitoring	
	7.4.	Protection Against Risks	
	7.3.	Followup for Serious Negative Reactions	
	7.2.	Serious Negative Reactions and Serious Adverse Events	
	7.1.	Minimal Risk Determination:	
7	SA	FETY ASSESSMENTS	
	6.2	Data Linkages	
	6.1	Data Sources	
6	Da	ta sources and Elements	15
	5.2	Concomitant Interventions	
	5.1	Interventions, Administration, and Duration	

15	REFERENCES	27
16	APPENDICES	62

PRÉCIS

Study Title

METRICAL: Music & MEmory: A Pragmatic TRIal for Nursing Home Residents with ALzheimer's Disease

Objectives

To conduct a repeat parallel, pragmatic cluster randomized control trial (RCT) of personalized music for nursing home (NH) residents with moderate to severe dementia cared for in 81 NHs within four NH health care systems: PruittHealth, Good Samaritan Society, Vetter Senior Living, and CommuniCare (Terrapins Division).

Design and Outcomes

Aim 1 of this study is to use a train-the-trainer model to implement M&M in 27 facilities with ongoing monitoring of the program's adoption and acceptance by long-stay NH residents with Alzheimer's disease-related dementias (ADRD). Using the implementation guide developed during the R21, corporate leadership will provide step-by-step training and support to facilities in the intervention arm to include: setting achievable milestones, reviewing progress, and assisting with mid-course corrections. Implementation will be closely monitored by Brown through monthly conference calls with the corporations and the leadership at the participating NHs.

Aim 2 of this study is to estimate the impact of M&M on agitated and aggressive behaviors in NH residents with moderate to severe dementia. Agitated and/or aggressive behaviors are measured three ways: by interviewing staff about resident behaviors over time (primary outcome); through direct observation of residents when using and not using M&M (secondary outcome); and using available administrative data (secondary outcome). Other secondary outcomes include: other emotional states directly observed while the resident is using and not using M&M (anger, pleasure, alertness, sadness), antipsychotic use, antidepressant use, anxiolytic use, and depression. In this cluster RCT, the unit of random assignment is the facility, but the unit of analysis is the patient, clustered within the facility. The analytic approach we propose is based upon the cumulative likelihood of reductions in agitated and aggressive behaviors in a long-stay population with moderate to severe dementia, conditional upon survival to at least one post-intervention observation. Outcomes will be evaluated using a repeat parallel design, comparing wave 1 (intervention) and wave 2 (control) NHs (n=54) in the first study year, and wave 2 (intervention) and wave 3 (control) NHs (n=54) in the second study year. The repeat design allows for modification of the intervention delivery between waves to increase adherence. Since we do not expect the intervention to affect mortality, the comparison will be based on the last observed total agitation score among residents meeting eligibility criteria in the treated and control groups. All deaths among exposed and control populations will be routinely controlled and reported to the data safety and monitoring board for monitoring purposes. Facilities will be stratified by corporation, and balanced on baseline agitated and aggressive behaviors and number of eligible residents, prior randomization. Because we are interested in the effect of the intervention among those who use it, we will also conduct an as-treated analysis, using a technique described by multilevel-mixture analysis for analyzing cluster randomized data with non-compliance.

Aim 3 of this study is to examine factors associated with variation in providers' adherence to the implementation of M&M. We will adopt six distinct approaches to documenting implementation adherence: 1) research staff will survey NHs at baseline to assess the quality improvement infrastructure and performance improvement practices; 2) using a user-defined assessment, NH staff will document aspects of the process by which potentially-eligible residents are assessed for their ability to listen to the music, their music preferences, and the results of their initial trial of the music; 3) NH staff (with the help of research staff) will capture metadata about each song played, including a count of the replays, which will yield estimates of the degree of exposure to the intervention; 4) research staff will document NH staff participation and attendance at all training sessions; 5) research staff will conduct interviews with NH staff to identify barriers, facilitators, and best practices related to implementation; and 6) research staff will conduct an environmental scan while on-site to capture observable characteristics of implementation variation, such as storage and use of equipment and staff familiarity with intervention. Our analysis will quantitatively and qualitatively characterize facility variation in implementation measures based on the consolidated framework for implementation research (CFIR)

constructs.

Interventions and Duration

M&M is a personalized music program that uses portable music players to deliver individualized music to people with dementia. NH staff provide cognitively-impaired people with music playlists tailored to their personal history of music preferences. The program assumes that musical memories remain present and that personalized music can quell the anxiety and agitation stimulated by the confusion secondary to dementia. NHs randomized to the first wave will receive the intervention in the first study year and end participation in the study; NHs randomized to the second wave will serve as controls in the first study year and receive the intervention in the study year and receive the intervention in the second study year; and NHs randomized to the third wave will serve as controls in the second study year, we will collect primary data (repeat parallel design). In the third study year, we will only rely upon secondary data to conduct outcome analyses.

Sample Size and Population

Eligible facilities will have at least 15 long-stay residents with moderate to severe dementia, defined as a diagnosis of dementia and either a Brief Interview for Mental Status score \leq 12 or moderately or severely daily decision-making. Preliminary research and pilot data informs our estimates of the potential effect of M&M on any improvement in agitated and aggressive behaviors. Assuming an intra-class correlation (ICC) of 0.12 and 6 points reduction in the outcome variable of interest (staff reporting of resident agitated and/or aggressive behaviors), we need 24 NHs in each arm to be able to test our primary outcome with power of .8 with a two-tailed alpha of .05. Since we plan on recruiting 27 facilities per arm, we will have adequate power even if we encounter unforeseen circumstances.

STUDY TEAM ROSTER

Principal Investigator:

[name] Professor of Health Services, Policy & Practice Florence Pirce Grant University [name] for Gerontology and Healthcare Research Brown University, School of Public Health Providence, RI 02912 [contact] [contact]

Co-Investigators:

[name] Assistant [name] for Gerontology and Healthcare Research Health Services, Policy & Practice Brown University, School of Public Health [name] [contact] [contact] Role: project director, co-Investigator

[name] Associate Professor of Biostatistics Brown University, School of Public Health [name] [contact] [contact] role: co-Investigator, statistical design and analysis lead

[name] Associate Director, Center for Long-Term Care Quality & Innovation Associate Professor of Practice, Department of Health Services, Policy & Practice Center for Gerontology and Health Care Research Brown University, School of Public Health Providence, RI 02912 [contact] [contact] Role: co-Investigator, intervention committee lead, corporate liaison, supervises consultants

[name] Director of the Center of Innovation in Long Term Services and Supports (LTSS COIN) Associate Professor of Medicine Associate Professor of Health Services, Policy and Practice Brown University & Providence VA Medical Center [contact] Role: co-Investigator, implementation science lead

[name], MA Associate Professor of Health Services, Policy and Practice

Protocol, Version 3.0

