Table 1. Repeat Parallel Design

*Primary data collection conducted in Sequence 1 and Sequence 2 nursing homes during Period 1, and Sequence 2 and Sequence 3 nursing homes during Period 3

[figure not shown]
*Secondary data collection including Minimum Data Set (MDS) and medication order data collected in all periods for all sequences, even during the coronavirus.

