Facilities will be randomized within NH health care system strata. Within each health system, sites will be partitioned into triplets based on the Mahalanobis distance from the overall mean on the following key variables: percentage of eligible nursing home residents with any agitated or aggressive behavior (MDS Aggressive Behavior Scale > 0) on their most recent quarterly or annual assessment and number of eligible long-stay residents. The rationale for this additional balancing is that agitated and aggressive behaviors, a study outcome of interest, are known to vary considerably at the facility-level due to nursing home resident composition, staffing, and the degree of "ascertainment" and documentation of behaviors. It was also important to balance on the number of eligible residents in a nursing home, because nursing homes with more eligible residents can be more selective in who receives the program, possibly picking "better" candidates. Within balanced triplets, one facility will be randomly chosen for each of three periods (Table 1).

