Agitated and aggressive behaviors. The Agitated Behaviors Mapping Instrument (ABMI). The ABMI has 14 items which can be collapsed into total agitation, verbal agitation, and physical agitation.(90) Interrater reliability (IRR) for identification of behavior exceeds 90% in Cohen-Mansfield's publications (93%, 96%); reported intraclass correlations coefficient (ICC) .90.(90-92) Cohen-Mansfield also reports high ICCs between videotaped (blinded) coding of behaviors and direct observation of behaviors (not blinded): .94 for verbal agitation, .93 for physical nonaggressive agitation, and .94 for total agitation.(90) Pearson correlation coefficients for identical items on the ABMI and CMAI are: .317 for verbal agitation (requests for attention .372, screaming .432, cursing .168, and complaining .442); .389 for physical agitation (pacing .542, repetitions .555, and exit seeking .322); .203 for combined agitation; .411 for physical aggression and .400 for disruptiveness.(93)

Mood. Mood states are also observed using the Lawton Observed Emotion Rating Scale (OERS),(85) which was designed to measure pleasure, anger, anxiety/fear, sadness, and general alertness in nursing home residents with ADRD.

Secondary Data

Agitated and aggressive behaviors. In addition to the CMAI and the ABMI, we will also measure agitation and aggressive behavior using the MDS. The Aggressive Behavior Score (ABS) is derived from four items in MDS, Section E, which describe the frequency of: 1) physical behaviors (hitting kicking, pushing, etc.); 2) verbal behaviors (threatening, screaming, cursing, etc.); 3) other behaviors (scratching self, pacing, throwing, smearing food, etc.); and 4) rejection of care. Each behavior problem is rated in its frequency, ranging from 0 (never) to 3 (daily), and the ABS is constructed by summing these four items. It has an alpha reliability between 0.79 and 0.93.(95)

Receipt of antipsychotic medications and their substitutes. We have two data sources for receipt of antipsychotic, antidepressant, and anxiolytic medications: electronic medication orders and the MDS. The MDS assessment includes a count of the number of days in the last 7 in which an antipsychotic, antidepressant, and anxiolytic medication was received. We are also receiving standing medication orders from all four corporations. This data includes drug name and class, order date, ordering physician, and number of pills.

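### For the MDS and medication-order outcomes in Period 1, the stated comparison leaves out the 27 Sequence 3 homes, half of the randomised controls whose data are already collected

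*Combined protocol and SAP*

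**What the plan says.** The Précis (Design and Outcomes, Aim 2) names the staff-interview score as primary. Its secondary outcomes include agitation from administrative data, antipsychotic, antidepressant and anxiolytic use, and depression. Without separating these by data source, it then says outcomes will be evaluated by "comparing wave 1 (intervention) and wave 2 (control) NHs (n=54) in the first study year", and by wave 2 versus wave 3 (again 54 homes) in the second year. Under Interventions and Duration, "NHs randomized to the third wave will serve as controls in the second study year"; no first-year role is given to them.

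Section 3, Table 1, lists Sequence 3 as a control in Period 1 with 405 residents. Its footnotes distinguish two kinds of data:

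- Primary data: "Primary data collection conducted in Sequence 1 and Sequence 2 nursing homes during Period 1", with Sequences 2 and 3 covered in Period 3.
- Secondary data: "Secondary data collection including Minimum Data Set (MDS) and medication order data collected in all periods for all sequences".

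Section 9.4.2 confirms that the medication outcomes need no site visit: "We have two data sources for receipt of antipsychotic, antidepressant, and anxiolytic medications: electronic medication orders and the MDS". The aggressive behaviour score and PHQ-9 also come from the MDS. Section 4.3.3 forms triplets within each corporation and randomises one home of each triplet to each sequence. Section 9.5 models the staff-interview score only. It gives no model or analysis set for the MDS or medication-order outcomes.

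On Sequence 1, the Précis says "NHs randomized to the first wave will receive the intervention in the first study year and end participation in the study", whereas Table 1 labels it as intervention, with 405 residents, in Period 3.

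**The concern.** In Period 1, Sequence 3 is concurrent, randomised and untreated, and its secondary data are collected. For the MDS and medication-order outcomes it is as good a control as Sequence 2, yet the only comparison the plan states omits it. The effect estimates for these Aim 2 secondary outcomes would then be less precise than the data allow.

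The plan also leaves room for choice. Table 1 suggests one control group and the Précis another, and Section 9.5 does not settle it. With the first trial finished, an unspecified control group could be chosen after the data are seen.

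**Working it through.** **The plan's own figure.** Section 9.2 gives SD 20, ICC 0.12, baseline to follow-up correlation 0.5, a 6-point difference, 80% power and alpha 0.05 (two-tailed in the Précis). Table 1 implies 405/27 = 15 residents per home.

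- Inflation factor: (1 + 14 × 0.12) × (1 − 0.5²) = 2.68 × 0.75 = 2.01.
- Residents per arm: 2 × (1.960 + 0.842)² × 20²/6² × 2.01 = 350.6.
- Homes per arm: 350.6/15 = 23.4, rounded up to 24. This matches the plan.

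**Homes left out.** For Period 1 secondary data, 27 of 81 homes are omitted (one third), which is 27 of the 54 control homes (one half).

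**Change in precision.** With equal cluster sizes, the variance of the contrast is proportional to 1/k(intervention) + 1/k(control).

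- 27 v 27: 1/27 + 1/27 = 2/27.
- 27 v 54: 1/27 + 1/54 = 1.5/27.
- Variance ratio: 1.5/2 = 0.75. SE ratio: √0.75 = 0.866, a fall of 13.4%.
- Within a triplet, one intervention home against the mean of two controls gives (1 + 1/2)/(1 + 1) = 0.75, so the result fits the randomisation.

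This ratio does not depend on the SD or ICC, which matters because the plan gives neither for these outcomes.

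**Power**, for the same true effect: Φ[(z at current power + 1.960)/0.866 − 1.960].

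- From 80%: Φ(2.802/0.866 − 1.960) = Φ(1.275) = 89.9%.
- From 60%: Φ(2.213/0.866 − 1.960) = Φ(0.596) = 72.4%.

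**Scale only.** On the CMAI planning inputs, the SE would go from 1.99 to 1.73 and the detectable difference from 5.58 to 4.83 points. For a binary medication outcome I assumed 24% prevalence (Table 2 shows 18% to 26% for antipsychotics), no baseline adjustment, ICC 0.05 to 0.20 and 15 to 50 residents per home. The detectable difference then goes from 8.6–16.4 to 7.4–14.2 percentage points.

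**Sensitivity to the cohort.** Suppose the analysis would otherwise use 15 site-listed residents per home, and the MDS-defined cohort has 30, of whom 15 are treated (assumptions; ICC 0.12).

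- Variance per home relative to plan: (4.48/30)/(2.68/15) = 0.836.
- With Sequence 3 added: 0.836 × 0.75 = 0.627, so the SE ratio is 0.792.
- If the average effect halves, 80% power becomes Φ(2.802 × 0.5/0.792 − 1.960) = 42%.
- The same MDS cohort at 27 v 27 (SE ratio 0.914) gives Φ(2.802 × 0.5/0.914 − 1.960) = 33%.

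The loss here comes from the broader cohort. For a given cohort, adding Sequence 3 still helps.

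**The case against.** **No passage bars Sequence 3.** This stands. The omission follows from a general sentence in the Précis, and Table 1 can be read as already giving Sequence 3 a control role. But the sentence follows directly on the list of secondary outcomes, it is the only comparison stated, and Section 9.5 does not correct it.

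**Timing.** This also stands. Section 9.2 says the first parallel trial finished just before the pandemic and uses its data for a post hoc power calculation. Changing the control group now is more than a wording edit and must be labelled as a change.

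**Unchanged effect.** The power gain assumes the same residents are analysed. Section 10.1 has homes list residents using, or likely to use, the music, and Sequence 3 has no such visit in Period 1. Sections 3 and 4.1 do identify eligible residents from the MDS, so the broader cohort may already be intended, but the documents do not settle this.

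**Stronger readings.** A reader might infer that a third of the homes are wasted. They are not: Sequence 3 is the control in Period 3. A reader might also infer that counting Sequence 1 as an intervention arm would dilute the Period 3 effect. The Précis already limits the second-year comparison to wave 2 versus wave 3. Nor can the 60% annual mortality in Section 7.2 be used to estimate how many Sequence 1 residents remain. It comes from another trial and would require a closed cohort, whereas Table 1 shows 405 residents per sequence in both trial periods.

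**Conclusion.** The concern holds as a loss of precision in Period 1 for the MDS aggressive behaviour score, antipsychotic, antidepressant and anxiolytic use, and PHQ-9. The 27 v 27 contrast remains a valid randomised comparison, so there is no bias, and the primary outcome is unaffected. Including Sequence 3 cuts the variance by a quarter, provided that cluster sizes are equal and the resident cohort is the same. The absolute power for these outcomes cannot be computed from the documents.

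On Sequence 1 in Period 3, what stands is a conflict of labels: Table 1 calls these homes intervention, while the Précis says they end participation after the first year and gives them no place in the second-year comparison. Section 5.1 lets homes keep the devices and encourages further use, so the label may describe continued use, but the plan should say so.

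**What to change.** 1. In the Précis, limit the 54-home Period 1 comparison to outcomes from primary data.
2. For MDS and medication-order outcomes, specify Sequence 1 (27 homes) versus Sequences 2 and 3 together (54 homes) in Section 9.5. The analysis should respect corporation strata and triplets and use one MDS-defined eligible cohort in all three sequences.
3. Date the change, state whether the Period 1 secondary outcomes had been examined by then, and report the 27 v 27 comparison alongside.
4. Reconcile the Sequence 1, Period 3 label in Table 1 with the two Précis statements, and say whether those homes enter any comparison in that period.

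The cost is an amendment and some added analysis; no new homes, visits or data are needed. The downside is that, if site-listed residents would otherwise have been analysed, the broader MDS cohort may dilute the effect and reduce or outweigh the gain in precision. The choice of cohort should therefore be stated and justified in the amendment.

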1 STUDY OBJECTIVES

Over 80% of people with Alzheimer's disease-related dementias ADRD exhibit behavioral and psychological symptoms of dementia (BPSD)(1, 2) that can adversely affect their experiences and outcomes.(3) BPSD are a heterogeneous group of symptoms ranging from agitation and anxiety to apathy, depression, delusions, and sleep or appetite changes.(2) BPSD not only adversely affects people's experiences and outcomes,(3) but also contributes to burden and stress for family caregivers(4-7) and healthcare providers.(8, 9) Use of antipsychotic medications to mitigate BPSD in ADRD increases the risk of serious complications,(10, 11) including extrapyramidal symptoms,(12-14) serious cardiovascular events,(14, 15) and even death.(16-18)(19) For this reason, existing guidelines recommend exhausting non-pharmaceutical options for treating these symptoms before initiating medications.(20, 21) Indeed, decreasing the use of antipsychotics for NH residents with dementia is a Centers for Medicare & Medicaid Services (CMS) goal.(22)

Eliciting musical memories using familiar or preferred music may decrease feelings of isolation and anxiety, (23, 24) as musical memories are encoded in areas of the brain affected later in the ADRD process than areas of the brain involved in verbal memory and executive functioning. (25, 26) (27-29) Studies have demonstrated that individualized music can reduce anxiety, (30-32) decrease negative affect or depression, (30, 31) and mitigate physically-agitated behaviors (33, 34) in people with ADRD. One specific music intervention, MUSIC & MEMORYSM (M&M), provides people with ADRD with iPods populated with music playlists tailored to their personal history of music preferences. (35) The purpose of METRICAL is to test the impact of implementing M&M on NH residents' BPSD outcomes during a four-year R33, by undertaking a pragmatic trial in four multi-facility NH corporations caring for residents with ADRD. We will conduct two parallel, cluster randomized controlled trial (RCT) with 81 facilities. The Specific Aims of the R33 are to:

Aim 1. Use a train-the-trainer model to disseminate M&M to 81 NHs, with ongoing monitoring of the program's adoption and acceptance by long-stay NH residents with ADRD.

Aim 2. Estimate the impact of M&M on agitated and aggressive behaviors, observed emotional states, antipsychotic use, antidepressant use, anxiolytic use, and depression for long-stay NH residents with ADRD.

Aim 3. Examine factors associated with variation in NHs' implementation of the implementation of M&M.

2 BACKGROUND AND RATIONALE

2.1 Background on Condition, Disease, or Other Primary Study Focus

ADRD(36-38) is the sixth leading cause of death and the only one in the top 10 that cannot be prevented, cured, or slowed.(39) Its prevalence is increasing with population aging and is expected to reach 7.1 million people by 2025—a 40% increase.(39) The Aging, Demographics, and Memory Study, a nationally representative sample of older adults, estimates ADRD prevalence at 5% for adults aged 71-79 years of age, rising to 24% for adults aged 80-89 years, and 37% for adults aged ≥90 years.(40)

Because of its effect on memory and other cognitive functions, ADRD leads to a loss of independent function that profoundly impacts patients, caregivers, and the healthcare system as a whole.(40) A significant number of people with ADRD require long-term services and supports (LTSS): the Centers for Disease Control and Prevention estimates that ADRD patients comprise nearly one-third of people receiving adult day (32%) or home health services (30%) and half of those living in assisted living (40%), hospice (44%), or NHs (49%).(41) Analyses of Medicare data, made publicly available through Brown's Long-term Care Focus website [http://ltcfocus.org/] suggest that 60% of long-stay NH residents have ADRD. Moreover, almost all people with ADRD exhibit BPSD over the course of their illness.(2, 3) The prevalence of BPSD is nearly 2.5 times as high among those in NHs (80%-96%)(1, 2) vs. the community (33%).(42) BPSD are a heterogeneous group of symptoms ranging from agitation and anxiety to apathy, depression, delusions, and sleep or appetite changes.(2) The pathogenesis is not well understood, although likely due to multifactorial causes.(2) BPSD not only adversely affects people's experiences and outcomes,(3) but also contribute to burden and stress for family caregivers(4-7) and healthcare providers.(8, 9)

BPSD-related problems contribute to high use of antipsychotic medications among NHs. CMS data reveal that, on average, 20% of long-stay NH residents are prescribed antipsychotics for BPSD symptoms.(43) A

2011 Office of the Inspector General (OIG) report found that 83% of NH antipsychotic use was off-label, and 88% of off-label use targeted residents with ADRD.(44) While antipsychotic use in NHs has decreased since 2012, likely as a result of the OIG report,(44) national efforts,(45, 46) and quality improvement (QI) campaigns,(47) prevalence remains high in light of the well documented adverse effects. Indeed, a 2011 systematic review documented the fact that antipsychotics increase the risk of cerebrovascular adverse events and death in this population.(48)

